5.1 Primary Objective

The objective of the trial is to test the efficacy of treatment with Pembrolizumab and Rituximab in patients with MZL in need of treatment, who have failed or are not eligible for local therapy or relapsed. For efficacy the rate of complete remissions (according to the GELA criteria for gastric MALT or to the Cheson 2007 criteria for nodal and splenic MZL) after end of treatment (18 cycles) will be primarily analyzed.

5.2 Primary Endpoint

Primary endpoint is the complete response (CR rate (CRR) determined after end of treatment (18 cycles). Patients who progress before EOT will be treated as CR='NO' and will be included in the calculation of the primary endpoint. No primary endpoint will be determined for patients who withdraw. These patients will be excluded from the confirmatory data analysis but will be analyzed in a separate exploratory sensitivity analysis of the primary endpoint.

For further information about the statistical analysis of the primary endpoint, see section 12.

5.3 Secondary Endpoints

The following parameters are the secondary endpoints:

- **Response rate**
The response rates (complete response (CR), partial response (PR)) and overall response rate (CR or PR) are evaluated 4 weeks after the end of treatment.
- **Best response**

Best response is determined in the time interval from the start of therapy to end of follow-up

- **Time to best response**

Time to best response is defined as the time from the start of therapy to best response the patient achieves (CR, PR)

- **Time to first response**

Time to first response is defined as the time from the start of therapy to first response (CR, PR).

- **Progression free survival (PFS)**

Progression free survival (PFS) is defined as the time from registration to the first occurrence of progression or relapse as assessed by the investigator, or death from any cause. PFS for patients without disease progression, relapse, or death will be censored at the time of the last tumor assessment.

- **Time to treatment failure (TTF)**

Time to treatment failure (TTF) is defined as the time of registration to discontinuation of therapy for any reason including death from any cause, progression, toxicity or add-on of new anti-cancer therapy. Patients alive without treatment failure are censored at the latest tumor assessment date.

- **Duration of Response (DR)**

Duration of Response will be calculated in patients with response (CR, PR) to therapy from diagnosis of response to the date of progression, relapse or death from any cause. Patients alive without progression and relapse will be censored at the latest tumor assessment date or the stopping date.

- **Cause specific survival (CSS)**

Cause specific survival is defined as the period from the study registration to death from lymphoma or lymphoma related cause; death unrelated to MZL is considered as a competing event.

- **Overall survival (OS)**

Overall survival is defined as the period from the induction registration to death from any cause. Patients who have not died until the time of the analysis will be censored at their last contact date.

- **Quality of life during trial**

Quality of life will be measured by the FACT Lym (see Appendix I) before start of treatment and during trial participation.

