6.1 Estimated Study Duration

It is expected that a total of 56 patients at approximately 15 investigator trial sites in Germany and 3 trial sites in Austria will be registered. Every patient will receive treatment over a time period of 18 cycles (each cycle lasts 3 weeks). Subsequently, patients will be monitored every 3 months for 2 additional years, subsequently every 6 months for three additional years.

Patients will be recruited over a period of 12-18 months.

1st patient registered (estimated): Q3 2020

Last patient registered (estimated): Q1 2022

Maximal duration of study therapy/patient: 18 cycles

(18 cycles with 21 days = 378 days resp. 54 weeks)

Duration of follow-up/patient: up to 5 years (until End of Study is reached)

End of study: LPLV 7.5 years (=90 months) after the first patient is included in the study

Considering a recruitment period of 12 – 18 months and a treatment period of 54 weeks, after 7.5 years all patients will either be in Follow-Up or will already have completed Follow-up. In the 90th month after FPI Follow-up Visits that were scheduled for this month can still take place. Sites will be notified in advance about EOS so that they can plan the Follow-up visits accordingly.

After finishing all study relevant procedures, therapy and follow-up period, the patient will be followed in terms of routine aftercare and treated if necessary by the primary responsible hematologic-oncologic center.

7. Study Population

Patients must have a proven pathological diagnosis of MZL, diagnosed by a reference pathology center.

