In patients with gastric extranodal MZL, the initial staging should include a gastroduodenal endoscopy with multiple biopsies from the stomach, duodenum, gastroesophageal junction, and any site that seems abnormal and must not be older than 12 weeks before start of treatment. If any disease sites are identified in this manner at screening, a subsequent gastroduodenal endoscopy and biopsy are required to confirm a CR. In addition, if other sites are involved at baseline, they should be appropriately staged at baseline and re-evaluated during follow-up. For response evaluation endoscopy should be performed at C10D1 and at the end of treatment. H. pylori status must be evaluated. Endoscopic ultrasound to evaluate the regional lymph nodes and gastric wall infiltration should be performed.

In patients with non-gastric extranodal MZL, the initial staging should be adapted to the affected site as follows and according to local practice:

- Small intestine (immunoproliferative small intestinal disease, IPSID): Campylobacter Jejuni search in the tumor biopsy by polymerase chain reaction (PCR), immunohistochemistry or in situ hybridization may be carried out.
- Large intestine: colonoscopy.
- Lung: Bronchoscopy + bronchoalveolar lavage.
- Salivary glands: Ear/nose/throat examination and ultrasound. To eliminate association with Sjögren syndrome anti-SSA or anti-SSB antibodies should be investigated.
- Thyroid: echography ± computer tomography (CT) scan of the neck and thyroid function tests.
- Ocular adnexa: MRI (or CT scan) and ophthalmologic examination. Chlamydia psittaci in the tumor biopsy and blood mononuclear cells by PCR may be considered.
- Breast: mammography and MRI (or CT scan).
- Skin: Borrelia Burgdorferi in the tumor biopsy by PCR (in endemic areas) may be considered.

For all patients with extranodal MZL the MALT-IPI should be determined. It is the decision of the investigator to conduct a FDG-PET-CT. Investigations must not be older than 12 weeks before start of treatment. If any disease sites are identified in this manner at screening, a subsequent investigation is required to confirm a CR. For response evaluation investigations should be performed at C10D1 and at the end of treatment.

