Patients who complete Cycle 9 will be asked to return to the clinic within 4–6 weeks after Cycle 9 Day 1 for C10D1 visit. Patients who discontinued treatment early will be asked to return to the clinic for Early Termination Visit. An early termination visit should occur within 4–8 weeks after last dose (in case of early termination due to adverse event) or within 2–8 weeks after last dose (in case of early termination due to clinical disease progression). Please see the Study Flowcharts provided in Appendix A for schedules of assessments to be performed at the induction completion/early termination visit.

The following assessments should be performed on Cycle 10 Day 1 before receiving study drug or on Early Termination Visit unless otherwise specified in the protocol:

- In patients with gastric extranodal MZL: Gastroduodenal endoscopy
- Tumor Assessment: by CT/PET-CT/MRI and/or Bone Marrow aspirate and biopsy and/or Immunophenotyping PB and BM
- Complete physical examination, including vital signs
- ECOG Performance Status
- Laboratory:
 - Quantitative Immunglobulins (IgA, IgG, IgM)
 - Serum Protein Immunofixation if initially positive for monoclonal Ig

- Leukocyte immunophenotyping (FACS) PB (and Bone Marrow Aspirate);
- Hematology
- Serum Chemistry and electrophoresis
- Coagulation
- HBV DNA PCR in patients who are HBsAg negative and HBcAb positive
- Urinalysis (dipstick). Microscopy as clinically indicated
- Urine Protein to Creatinine Ratio (UPCR) measurement when clinically indicated
- GFR
- Women of childbearing potential: negative urine pregnancy test
- 12-lead ECG and an echocardiography when clinically indicated
- Safety assessment (see Section 8.3 and 11).
- Concomitant medication review. Please note: contrast media does not need to be recorded as concomitant medication unless there is an AE related to its administration (e.g. allergic reaction).
- In case of Early Termination Visit: new anti-lymphoma treatment

Please see the Study Flowcharts provided in Appendix A for schedules of assessments to be performed during Treatment phases.

Patients with at least SD will continue study treatment as specified above until end of cycle 18 or until PD is determined.

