Appendix A: Study Flowchart

Treatment – Phase

	Section	Screening	Treatment Period (1 cycle = 21 days)						EOT/ ET Visit (4 weeks after C18/D1)
		SD -28	C1/D1	C1/D2	C1/D8 + D15	C2/D1 – C9/D1	C10D1	C11/D1 – C18/D1	
Informed consent incl. discussion of fertility issues and sperm banking (in patients of childbearing age)*	10.1	X							
Verify Inclusion/exclusion criteria*	7.1 + 7.2	X	X						
Pathological diagnosis (local and reference pathology – incl. MYD88 and PD-L1*)	9.1.1	Within 12 months before C1D1							
Demographics, Medical history and Ann Arbor Stage*	9.1.4	X							
Patients with gastric extranodal MZL: Gastroduodenal endoscopy ^a	9.1.2	Within 12 weeks before C1D1					X ^c		X ^c
Patients with non-gastric extranodal MZL: Assessments according section 9.1.2	9.1.2	Within 12 weeks before C1D1					X ^c		X ^c
Bone marrow aspirate and biopsy ^b	9.1.3	Within 12 weeks before C1D1					X ^b		X ^b
CT/MRI scan and tumor assessment	9.1.2	Within 6 weeks before C1D1					X ^c		X ^c
12-lead ECG + Echocardiography	9.1.9	X					X ^d		X ^d
B Symptoms	9.1.6	X	X			X ⁱ	X ⁱ	X ⁱ	X
Physical examination ^e	9.1.5	X	(X)			(X)	X	(X)	X
Vital signs	9.1.7	X	X	X	X	X	X	X	X
ECOG Performance Status*	9.1.8	X	X			X	X	X	X
Concomitant medication	9.3 – 9.4	X	X	X	X	X	X	X	X
Adverse events / Toxicity	11		X	X	X	X	X	X	X

Treatment – Phase (continued)

	Section	Screening SD -28	Treatment Period (1 cycle = 21 days)						EOT/ ET Visit (4 weeks after C18/D1)
			C1/D1	C1/D2	C1/D8 + D15	C2/D1 – C9/D1	C10D1	C11/D1 – C18/D1	
Laboratory Assessments	9.1.10								
HIV, HBV, HCV testing ^f	9.1.10	X				X ^f	X ^f	X ^f	X ^f
Pregnancy test	9.2 – 9.4 + App. C	X	X			X	X	X	X
Hematology	9.1.10	X	X		X	X	X	X	X
Serum chemistry ^{g, h}	9.1.10	X	X		X	X	X	X	X
Electrophoresis (If M Protein present: add. Serum Protein Immunofixation)	9.1.10	X	X		X	X	X	X	X
Coagulation	9.1.10	X				X	X	X	
Thyroid hormones	9.1.10	X				X ^m	X ^m	X ^m	
Leukocyte immunophenotyping (FACS) ^j	9.1.10	X					X		X
Quantitative Immunoglobulins (IgG, IgA, IgM)	9.1.10	X					X		X
Urine analysis ⁱ	9.1.10	X				X ⁱ	X ⁱ	X ⁱ	X ⁱ
UPCR	9.1.10	X	X ^d		X ^d	X ^d	X ^d	X ^d	X ^d
GFR (acc. MDRD formula)	9.1.10	X				X	X	X	X
QoL questionnaire (FACT-Lym)*	9.1.11		X			X (Day 1 of every third cycle)			X
Tumor tissue sample at time of relapse or transformation	9.1.2					(X) ^k			
New anti-lymphoma treatment	9.5								X
Biological Material for Biobank (optional)*	9.1.12 + App. B	X					X		X

Treatment – Phase (continued)

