Details for d): Time to first response is defined as the time from the start of therapy to first response (CR, PR). For calculation, the difference between the date of the first day of treatment in cycle 1 (*C1/D1*; see CTP pages 106-110) (variable *EXSTDAT* for *ACTIVITYID* = '*C1D1_SV*' in table **EX1**) and the date of first response (first date at which CR or PR is reached) will be used. For the determination, the variable *THERAPY_RESULT* (see section 'Details for b)' above) will be used, together with the date of assessment which is calculated as variable *ASS_DATE* from the variables *RSDAT_NMZEG*, *RSDAT_EGM* and *RSDAT_SMZ* in table **RS**. Patients who reach CR or PR: The earliest date at which CR or PR is documented will be determined for each patient across all points in time with tumor assessment and will be used as end date for time to first response (not censored). Patients who do not achieve the response category CR or PR, will be censored at the latest tumor assessment date.

Details for e): Progression free survival is defined as the time of registration to the first occurrence of progression or relapse as assessed by the investigator, or death from any cause. PFS for patients without disease progression, relapse, or death will be censored at the time of the last tumor assessment. Progression free survival will be calculated as difference between time of registration (date of patient signed written informed consent; variable *RFICDAT* in table **DM**) and the earliest date of the event (progression or relapse or death) or the date of last tumor assessment (in case of no event). For the earliest date in case of progression or relapse the dates in table **RS** will be used as follows: nodal MZL and extragastric MALT lymphoma: variable *RSDAT_NMZEG* for *RSORRES_NMZEG* = 4, extranodal gastric MALT lymphoma: variable *RSDAT_EGM* for *RSORRES_EGM* in (4 5), splenic MZL: variable *RSDAT_SMZ* for *RSORRES_SMZ* = 4. Additionally for the date of progression, the variable *RSDAT_ET* (table **DSET** IF *DSDECOD_ET* = 3) will be used for identifying patients with PD. For patients who died, the date of death will be determined using the variable *DTHDAT* in table **DSEOS**.

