8.2.3 Efficacy Analysis of Secondary Endpoints

All secondary endpoints (Response rate, Best response, Time to best response, Time to first response, PFS, TTF, DR, CSS, OS and Quality of life during trial (therapy)) will be analysed exploratory by respective descriptive analysis, statistical tests and two-sided 95%-confidence intervals. Missing values will not be replaced.

Response rate and best response: The rates incl. the two-sided 95% confidence intervals (Clopper-Pearson) will be provided. The confidence limits can be used for a comparison with a fixed value.

Time to best response, time to first response, PFS, TTF, RD, CSS, OS: Kaplan-Meier plots will be provided. Because time to best response and time to first response describe a favourable event, the ordinate of the Kaplan-Meier plot will be "1 minus survival probability" instead "survival probability".

Quality of life during trial: The FACT-Lymphoma Trial Outcome Index (TOI), the FACT-G total score, the FACT-Lymphoma total score and the sum score for each of the five subscales (PWB, SWB, EWB, FWB, LYMS), will be analysed as continuous variable.

With exception of the efficacy analysis of the primary endpoint, each statistical test will be performed two-sided at a significance level of 5%. All results from these analyses will be regarded as hypothesis generating only and not as proof of efficacy.

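### Response is staged on schedule only at weeks 27 and 55, but time to first and best response are analysed as exact times, so the location of the Kaplan-Meier curves largely follows the visit calendar

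*Protocol*

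**What the plan says.** Both endpoints start at the first treatment day. Protocol 5.3 puts it this way for one of them: "Time to first response is defined as the time from the start of therapy to first response (CR, PR"). For the end date, SAP 7.5 c) and d) use the same sentence: "The earliest date at which CR or PR is documented will be determined for each patient across all points in time with tumor assessment". Such patients count as uncensored on that date. Patients without CR or PR are censored at their last assessment. SAP 8.2.3 then states "Time to best response, time to first response, PFS, TTF, RD, CSS, OS: Kaplan-Meier plots will be provided", with the two response endpoints drawn as one minus the survival probability.

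The on-treatment staging schedule is sparse:
- Gastric disease (Protocol 9.1.2): "For response evaluation endoscopy should be performed at C10D1 and at the end of treatment".
- Non-gastric extranodal disease (Protocol 9.1.2): "For response evaluation investigations should be performed at C10D1 and at the end of treatment".
- All patients (Protocol Appendix A): the row "CT/MRI scan and tumor assessment" is marked at baseline, C10D1 and EOT/ET, and is empty for cycles 2-9 and 11-18.

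Staging outside this grid comes from Early Termination visits (Protocol 9.3), suspected progression (9.1.2) and follow-up after EOT (9.5 and Appendix A).

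**The concern.** A patient first found in response at C10D1 responded at some unknown time between baseline and that visit. A patient first found in response at EOT responded between the two visits. The SAP replaces each interval by its right-hand end and treats that date as exact. Neither document mentions interval censoring or the width of the gaps.

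These two of the ten secondary endpoints are meant to describe how quickly patients respond. With gaps of about half a year, the horizontal position of the curve says little about that. A reader who takes a median from the plot would mostly be reading off the date of a visit. The exception visits add a distortion of their own, because someone who leaves treatment early is staged early.

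**Working it through.** **Inputs.** Cycle length and treatment duration: Protocol 6.1. Staging visits: Protocol 9.1.2, 9.3, 9.4 and Appendix A. Event date and display: SAP 7.5 c), d) and 8.2.3. Number enrolled, 22: SAP 2.1. Days are counted from C1D1.

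**Step 1, the plan's own figure.** Protocol 6.1 gives "18 cycles with 21 days = 378 days resp. 54 weeks". Check: 18 × 21 = 378 and 378 / 7 = 54. It reproduces.

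**Step 2, staging dates.**
- C10D1 from 21-day cycles: 9 × 21 = 189 days = week 27.
- C10D1 from Protocol 9.3, which asks patients to "return to the clinic within 4–6 weeks after Cycle 9 Day 1 for C10D1 visit": 8 × 21 + 28 = 196 days to 8 × 21 + 42 = 210 days, or weeks 28-30. The two passages disagree and must be reconciled.
- EOT, four weeks after C18D1: 17 × 21 + 28 = 385 days = week 55.
- Gaps: 189 days, then 385 − 189 = 196 days.

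**Step 3, error in one recorded time.** A true response on day t, with 0 < t ≤ 189, first documented at C10D1, is overstated by 189 − t. That is anywhere from 0 to 189 days. If true times were uniform over the gap (an assumption), the mean would be 189 / 2 = 94.5 days.

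**Step 4, what the curve can distinguish.** Assume, for illustration only, that a fraction p ever responds and that true times among them are exponential with median m weeks. The share documented in response by week 27 is p × (1 − 2^(−27/m)).

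| m (weeks) | Share by C10D1, p = 0.80 | Share by C10D1, p = 0.95 |
|---|---|---|
| 4 | 79% | 94% |
| 8 | 72% | 86% |
| 12 | 63% | 75% |
| 20 | 49% | 58% |
| 30 | 37% | 44% |

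The median over all patients falls at the first visit where the share reaches 50%. A simulation with n = 22, p = 0.80, visits varying by ±4 days and staging at weeks 27 and 55 only gave typical observed medians of 27.1, 27.2 and 27.3 weeks for m = 4, 8 and 12. For m = 30 it gave 55.0. For m = 20 it fell near week 27 in 53% of runs and near week 55 in most of the others. The time axis therefore does not separate true medians of 4 to 12 weeks. The step heights do differ.

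**Step 5, early termination.** Protocol 9.3 places this visit 4-8 weeks after the last dose when a patient stops for an adverse event, and it includes tumour assessment. With a last dose at C3D1 (2 × 21 = 42 days), staging falls on days 42 + 28 = 70 to 42 + 56 = 98. A responder found there is dated 91 to 119 days earlier than one staged at C10D1, even if both truly responded on the same day.

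**Step 6, time to best response.** SAP 7.5 c) first defines the date as the first CR or, without a CR, the first PR. It then sets the end date to the earliest CR or PR. For a patient in PR at C10D1 and in CR at EOT, the first rule gives day 385 and the second day 189. The second rule is the one in d), so applying it makes the two endpoints the same variable.

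**The case against.** A reader might infer that the curves can show nothing but the calendar. The documents do not support that. The height of each step estimates the share responding by that visit. The SAP uses every assessment, not two visits only. Early Termination staging can date a response before day 189. Later dates come from imaging six-monthly for two years and then yearly, and from three-monthly endoscopy while gastric disease persists. Treatment holds and cycle delays spread the C10D1 dates further.

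A reader might also infer that a median will be presented as a drug effect. Nothing in the text says so. SAP 8.2.3 promises plots for these endpoints, names no median, sets no comparator or reference value for them, and confines the secondary results to hypothesis generation. The median appears in SAP 8.1 as a general summary for continuous variables, where appropriate. That makes it a foreseeable output but not a planned claim.

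Other points in the plan's favour also stand. Any trial with periodic staging dates response at the visit; here the gap is simply long. The 12-weekly staging described in Protocol 4.3 belongs to a Hodgkin lymphoma study cited as background, and no comparison with it is planned. EOT response rates with Clopper-Pearson intervals are already in the SAP. With few distinct staging times, an interval-censored curve adds little to the response proportions by visit.

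What remains is that the SAP treats the staging date as the response date without saying so. The extra dates do not cure this, because early-termination dates depend on stopping treatment.

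**Conclusion.** The point holds as a minor one. For patients who stay on treatment without suspected progression, response before EOT is dated on a grid of 189 and 196 days. The location of both Kaplan-Meier curves is therefore driven largely by the schedule, and a median should not be read as speed of response. The staging dates rest on 21-day cycles without delay. The indistinguishability of 4 to 12 weeks also rests on the exponential model, the two assumed response fractions and no early termination in the simulation.

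The proposed proportions have limits too. At a share of 72% with 22 patients, the standard error is √(0.72 × 0.28 / 22) ≈ 0.096, or about 10 percentage points, so one trial of this size would not reliably separate the first three rows of the table. They do report what was observed, with honest uncertainty. The primary endpoint is not affected.

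**What to change.** In SAP 8.2.3:
1. Add the proportions in CR and in CR or PR at C10D1, with Clopper-Pearson 95% intervals, beside the EOT rates already planned. State how gastric patients count, since Protocol Appendix E asks for two successive negative investigations for CR.
2. If a time curve is kept, treat response time as interval-censored between the last staging without response and the first staging with response (for example PROC ICLIFETEST in SAS 9.4).
3. State that no scheduled staging precedes C10D1, that earlier dates arise from early termination or suspected progression, and that a Kaplan-Meier median is not interpreted as speed of response.

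In SAP 7.5 c), keep one definition of the date of best response, so that the endpoint either differs from time to first response or is dropped as a duplicate.

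The cost is some SAP wording and a short program, with no new scans or data. The downside is the loss of a familiar single median.
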